5 TREATMENT PLAN

Treatment will be administered on an outpatient basis. Expected toxicities and potential risks as well as dose modifications for isoquercetin are described in Section 6 (Expected Toxicities and Dosing Delays/Dose Modification).

Phase	Agent*	Isoquercetin Dose	Route	Schedule	Cycle
Phase II	Isoquercetin (IQC- 950AN) 250mg	Cohort A: 500 mg or Cohort B: 1000 mg	Oral capsules	Cohort A: 2 capsules once daily Cohort B: 4 capsules once daily	28 days
Phase III	Isoquercetin (IQC- 950AN) or Placebo	Cohort C: TBD or Cohort D: Placebo	Oral capsules	Once daily (TBD)	28 days

*All capsules (placebo and isoquercetin) include ascorbic acid 62 mg and niacin 5 mg.

Phase II

Cohort A: Patients will receive isoquercetin 500 mg once daily (2 capsules). Continued enrollment into the dosing cohort will be based on the safety evaluation of the initial 5 patients. If there are ≥ 1 grade 3 or 4 toxicity (possibly, probably or definitely related to isoquercetin), then decision to enroll an additional cohort of 25 patients will be based on DSMC recommendations. If there are ≥ 3 grade 3 or 4 adverse events (possibly, probably or definitely related to isoquercetin), the decision to proceed with enrollment into cohort B will be based on PSMC.

Cohort B: Patients will receive isoquercetin 1000 mg once daily (4 capsules). Similar to cohort A, continued enrollment will be based on the absence of attributable significant toxicities.

For both cohorts A and B, lower extremity ultrasound will be performed at end of treatment visit. Baseline D-dimer and correlative labs will be drawn at Day 1 and at end of treatment visit. Patients will be followed for survival after completion of end of treatment visit.

Phase III

Following the completion of the phase II portion, enrolled patients will be randomized 1:1 to Arm C (isoquercetin) or Arm D (placebo). The dose for Arm C will be determined after evaluation of the Phase II portion of the trial. The protocol will be amended when the decision is made whether to proceed to Phase III and what dose to use for Arm C. The study will be double-blinded to treatment arm. Lower extremity ultrasound will be performed at end of treatment. Baseline D-dimer and correlative labs will be drawn at Day 1 and at end of treatment. Patients will be followed for survival after completion of end of treatment assessment.

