14.1.1.5 Decision to proceed with enrollment into Cohort B

A sequential two-stage design will be employed in the Phase II portion of this trial, within each dose level, to evaluate the adverse events of major toxicity (probable or possibly related grade 3 or 4 adverse events including hemorrhage) at end of treatment for potential early termination of the dose in the case of excessive toxicity. After 5 patients have finished 56 days of therapy, the study will be placed on hold and toxicities evaluated. If more than one major toxicity is observed within the first 5 patients enrolled in Cohort A, the cohort will be suspended and detailed toxicity data reviewed for possible closure of the study to further accrual based on DSMC review. The probability of stopping accrual after the first 5 patients based on the true but unknown toxicity event for major hemorrhages is shown in the table below. If the study criteria are met to reopen the second stage, accrual will begin after the first 5 patients have finished study treatment and all toxicity data have been reviewed. With 5 eligible patients in the first stage, the probabilities of observing at least one toxicity with corresponding true rate of 1% and 5% are, respectively, 5% and 23%. With 30 eligible patients the respective probabilities of one or more events are 26% and 79%. The maximum width of a 95% confidence interval on any given toxicity, unadjusted for the two-stage design is 36%. Adjusting for the two-stage design, the maximum 95% confidence interval width would be 50%. If there are greater than 3 major toxicities in the 30 patients in Cohort A, then the cohort will be suspended and detailed toxicity data reviewed for possible closure of the study to further accrual based on DSMC recommendations. If the true but unknown toxicity event for major hemorrhages is 5% and 15%, the probability of proceeding to Cohort B after the evaluation of the 30 patients in Cohort A is 92.5% and 30.8%, respectively. A similar twostage design will be employed for patients enrolled in Cohort B. If there are more than 1 major toxicities in the first 5 patients or three or more

True attributable toxicity	0.05	0.1	0.15	0.2	0.25	0.3	0.35	0.4	0.45
Probability of stopping early after 5 patients	0.023	0.081	0.165	0.263	0.367	0.472	0.572	0.663	0.744
Probability of stopping at the end of the cohort A	0.075	0.373	0.692	0.883	0.964	0.991	0.998	0.999	0.999

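### The stated maximum two-stage 95% interval width of 50% does not follow from the stage 1 rule in Section 14.1.1.5: it is up to 80% if accrual ends at 5 patients and up to 66% in completed cohorts

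*Combined protocol and SAP*

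**What the plan says.** Section 14.1.1.5 describes a two-stage toxicity design within each Phase II dose level.

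- First look: "After 5 patients have finished 56 days of therapy, the study will be placed on hold and toxicities evaluated". The rule there is "If more than one major toxicity is observed within the first 5 patients enrolled in Cohort A, the cohort will be suspended", with data review for possible closure.
- Second look: "If there are greater than 3 major toxicities in the 30 patients in Cohort A, then the cohort will be suspended", again with review.
- Precision without adjustment: "The maximum width of a 95% confidence interval on any given toxicity, unadjusted for the two-stage design is 36" percent.
- Precision with adjustment for the two-stage design: "the maximum 95% confidence interval width would be 50" percent.

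No interval method is named for either width, and no ordering of outcomes is named for the adjusted one. The text does not say whether the adjusted maximum covers cohorts closed at 5 patients or only those that reach 30.

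Section 5 (Treatment Plan, Phase II, Cohort A) gives a different stage 1 trigger. With one or more related grade 3 or 4 toxicities among the initial 5 patients, the "decision to enroll an additional cohort of 25 patients will be based on DSMC recommendations".

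**The concern.** A stated maximum can be checked: one attainable outcome with a wider interval disproves it. Under the Section 14.1.1.5 rule a cohort can close with 2 to 5 toxicities in 5 patients, and five patients give little precision. Completed cohorts also need checking, because allowing for the early look widens the interval.

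These two sentences are the plan's only statement of how precisely toxicity will be estimated. At stake is whether the monitoring committee and readers of the Phase II report expect tighter estimates than the design can give. The chance of the five-patient case is not negligible: the plan's table puts stopping at 5 patients at 0.165 for a true rate of 15% and 0.472 for a rate of 30%.

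**Working it through.** **Inputs.** From Section 14.1.1.5: stage 1 of n₁ = 5, continue with 0 or 1 toxicities, total n = 30, two-sided 95% level. From Section 5: 25 further patients in stage 2. Let X₁ be the toxicities in the first 5 patients and S the total in 30.

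**1. The rule is read correctly.** P(X₁ ≥ 2) from the binomial, and 1 − P(X₁ ≤ 1, S ≤ 3), reproduce the plan's stopping table: 0.023 and 0.075 at a true rate of 5%, 0.165 and 0.692 at 15%.

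**2. The unadjusted 36%.** The Wald width is largest at 15/30: 2 × 1.96 × √(0.25/30) = 35.8%. The exact (Clopper-Pearson) interval at 15/30 is 31.3% to 68.7%, width 37.4%. The plan's figure is a normal approximation that is 1.6 points narrower.

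**3. Accrual ends at 5 patients.** When every stage 1 stop ranks above every completed cohort, the two-stage exact interval for a stopped cohort equals Clopper-Pearson at n = 5.

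| Outcome | Interval | Width |
|---|---|---|
| 2/5 | 5.3% to 85.3% | 80.1% |
| 3/5 | 14.7% to 94.7% | 80.1% |
| 4/5 | 28.4% to 99.5% | 71.1% |
| 5/5 | 47.8% to 100% | 52.2% |

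(Widths are from unrounded limits.) At 2/5 or 3/5 the mid-P interval is 74.4% wide and the Wilson interval 65.2%.

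**4. Cohorts completing 30, stage-wise ordering.** For an observed total s:

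- lower limit: the p that solves P(X₁ ≥ 2) + P(X₁ ≤ 1, S ≥ s) = 0.025
- upper limit: the p that solves P(X₁ ≤ 1, S ≤ s) = 0.025

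| Outcome | Interval | Width |
|---|---|---|
| 0/30 | 0% to 11.6% | 12% |
| 3/30 | 2.0% to 26.3% | 24.3% |
| 4/30 | 3.3% to 30.3% | 27.0% |
| 12/30 | 5.3% to 55.2% | 49.9% |
| 13/30 | 5.3% to 57.7% | 52.4% |
| 15/30 | 5.3% to 62.1% | 56.8% |
| 26/30 | 5.3% to 71.6% | 66.4% |

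The maximum has a simple source. For large s the lower limit tends to the p where P(X₁ ≥ 2) = 0.025 (5.28%), and the upper limit to the p where P(X₁ ≤ 1) = 0.025 (71.64%). The difference is 66.4%.

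**5. How likely is a completed cohort wider than 50%?** It needs S ≥ 13 after X₁ ≤ 1. The probability is 0.005% at a true rate of 15%, 0.08% at 20%, 1.9% at 30% and 8.1% at 40%.

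**6. The Section 5 trigger (1 or more of 5).** The limits for large s become 1 − 0.975^(1/5) = 0.51% and 1 − 0.025^(1/5) = 52.18%, so the full-cohort maximum is 51.7%; at 15/30 the width is 50.3%. A cohort ending at 2/5 or 3/5 still gives 80.1%.

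**7. Other routes to 50%.** Mid-P, a 90% level, totals of 26 or 35, stage 1 triggers of 3 or 4 events, stopping on the low side, and Bonferroni-type levels do not give a maximum of 50% under the Section 14.1.1.5 rule.

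**The case against.** The sentence most naturally describes 30-patient precision. It follows a statement about 30 eligible patients and a 36% that is purely an n = 30 figure. A reader might infer that the plan promises 50% for five patients; the text does not say so. Stopping at 5 is also suspension and review, not automatic closure. This stands, and it is why the completed-cohort result is needed. That reading still fails, from 13/30 upward.

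The completed-cohort widths rest on two conditions. The interval is meant for any given toxicity, whereas stopping is driven by a composite of related grade 3 or 4 events. The stage-wise figures apply to that composite and not directly to a single toxicity within or outside it. They also depend on the ordering: ordering by the observed rate gives up to about 80% in a completed cohort. Both limits stand and should be stated with the figures.

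The exceedance is remote, and 26/30 requires all 25 second-stage patients to have a major toxicity. At the boundary that matters, 3/30 or 4/30, a 50% ceiling is conservative. A reader might infer that the plan overstates precision wherever stopping is debated. That does not hold at the end-of-cohort look. At the five-patient look the decision rests on a count and committee review, with no interval used.

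A reader might also infer that the 36% is wrong. It is a correct normal-approximation width.

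**Conclusion.** The point holds as a minor inaccuracy. Under the Section 14.1.1.5 rule, 50% is not the maximum adjusted width on either reading: 80% if cohorts closed at 5 are included, and 66% for completed cohorts under stage-wise ordering of the major-toxicity composite. For the outcomes that allow continuation (0 to 3 of 30) the adjusted width is 12% to 24%. No threshold, sample size or table entry uses the 50%, and the stopping table reproduces.

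Two stronger conclusions are not supported. One is that no valid interval from five patients could be 50% wide or less: the plan names no method, so the result is limited to the methods checked. The other is that the 50% was computed from the Section 5 trigger. The near match (50.3% at 15/30, maximum 51.7%) makes this plausible, but the documents do not say how the figure was obtained. What is certain is that Sections 5 and 14.1.1.5 give different stage 1 triggers and that the completed-cohort width depends on which applies.

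**What to change.** 1. Reconcile the stage 1 triggers in Sections 5 and 14.1.1.5, then compute the widths for the rule that results. Which trigger is appropriate is for the sponsor and the monitoring committee.
2. Name the interval method and the ordering (for example, exact two-stage with stage-wise ordering), and say that the adjusted widths refer to the major-toxicity composite.
3. Replace the single 50%. If the Section 14.1.1.5 rule is retained: up to 80% if a cohort is stopped at 5, up to 66% for completed cohorts, and at most 24% when 3 or fewer of 30 have major toxicity.
4. Leave the 36% as it is; labelling it a normal approximation (exact 37.4%) would be enough.

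Restating the widths changes text only, with no effect on sample size or on how the widths are used. If reconciliation changes the stage 1 trigger in Section 14.1.1.5, its stopping table needs recomputing as well.

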14.1 Study Design/Endpoints

- 14.1.1 The primary endpoint of the Phase II trial is to investigate whether isoquercetin significantly reduces d-dimer values in cancer patients. D-dimer is a readily available biomarker used clinically in the prediction and diagnosis of VTE. In cancer cohorts, the D-dimer has modest specificity for predicting symptomatic thrombosis.⁵⁸ However, D-dimer remains the most validated surrogate marker of thrombin generation in vivo and symptomatic VTE.
 - 14.1.1.1 **Study Design**: The trial is a sequential cohort study of isoquercetin 500 mg and 1000 mg daily.
 - 14.1.1.2 Randomization: Patients will not be randomized.
 - 14.1.1.3 Accrual: Anticipated accrual is 10 patients per month across all study sites.

14.1.1.4 Sample Size Justification: Plasma D-dimer levels typically decrease at least 20% following the initiation of anticoagulation.⁵⁹ The sample size is based on a paired t-test of D-dimer concentrations measured on day 1 and end of treatment, to be performed separately for each arm. In the recently completed MicroTEC study, the median baseline D-dimer concentration for all cancer patients enrolled was 815 ug/L.⁴⁷ Based on an estimated standard deviation of 0.3 for the ratio of the D-dimer levels at day 56 over the D-dimer levels at day 1, a total of 26 subjects are needed per arm for a 90% power to declare the reduction significant if the true concentration at end of treatment is reduced by 20% in each isoquercetin arm (one-sided alpha 0.05). Estimated death or dropout of 5% prior to 56 days, the sample size will be increased to a total of total 30 per arm (onesided alpha 0.05). With 30 eligible patients per dose level, there is greater than 60% power to detect an unacceptable attributable grade 3 or 4 rate of 15% at 56 days using a one-sided 10% level exact binomial test in each dose level. (see table below)

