major toxicities in the 30 patients in Cohort B, then we will only consider proceeding to the phase III portion of the study with isoquercetin 500 mg daily.

- 14.1.1.6 **Primary endpoint analysis:** D-dimer concentrations will be compared for each patient at day 0 and end of treatment by a paired-t test analysis. Analysis will be performed on an intention to treat basis for patients who undergo randomization and completed the baseline and end of treatment D-dimer assessments.
- 14.1.1.7 Determination of continuation with phase III trial and selection of dose. Following completion of the phase II study, decision will be made by principal investigators whether to proceed with enrollment into the phase III trial. The decision to continue will be principally guided by whether either isoquercetin arm reached the primary endpoint definition. If both isoquercetin arms meet the primary endpoint then selection of dose will be based on degree of reduction in D-dimer levels in each arm relative to baseline and toxicity profile with special attention to major hemorrhage episodes. If neither isoquercetin arm results in significant reduction in d-dimer values relative to baseline, then consideration to advance to phase III will be made based on overall VTE rate in the combined isoquercetin arms. D-dimer is a recognized biomarker of the prothrombotic state but is known to lack specificity in cancer cohorts⁵⁸. Because it is possible that isoquercetin is an effective antithrombotic without altering plasma D-dimer values especially considering potential antiplatelet activity, we will also analyze the cumulative incidence of VTE collectively for the isoquercetin treated patients. A true cumulative incidence VTE rate of less than 10% would be considered promising in the combined isoquercetin arms, whereas a true cumulative incidence rate of 25% would not be worthy of further study. Treatment is considered promising among the 60 patients treated with isoquercetin when nine or fewer VTE are observed. This design has at least a 92% chance of concluding the treatment is effective when the true cumulative incidence

rate is 10%, and less than a 5% chance of concluding the treatment is effective when the true cumulative incidence rate is 25% or more (Fisher exact test). If determination to proceed to phase III is based on promising VTE rates, then the higher dose level of isoquercetin will be utilized.

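### Cohort A's full-cohort toxicity limit appears to be applied only once 30 patients are in; suspending accrual at the event that crosses it leaves the printed stopping probabilities unchanged

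*Combined protocol and SAP*

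**What the plan says.** Section 14.1.1.5 describes a two-stage toxicity design within each dose level, meant to allow a dose to be ended early if toxicity is excessive.

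- **First look, Cohort A:** "After 5 patients have finished 56 days of therapy, the study will be placed on hold and toxicities evaluated". Then: "If more than one major toxicity is observed within the first 5 patients enrolled in Cohort A, the cohort will be suspended", with review by the data and safety monitoring committee (DSMC).
- **Second look, Cohort A:** "If there are greater than 3 major toxicities in the 30 patients in Cohort A, then the cohort will be suspended", again for DSMC review and possible closure. The matching table row is the "Probability of stopping at the end of the cohort A". The text gives the chance of going on to Cohort B (92.5% at a true rate of 5%, 30.8% at 15%) as of the time when the 30 patients have been evaluated.
- **Cohort B:** a similar two-stage design is announced, but the consequence differs. With more than one event in the first 5, or three or more "major toxicities in the 30 patients in Cohort B, then we will only consider proceeding" to phase III at the Cohort A dose.

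Section 5 rests continued enrolment in Cohort A on the first 5 patients. It attaches a later count to the next cohort: "the decision to proceed with enrollment into cohort B will be based on PSMC".

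Section 12.2 has the DSMC review toxicity up to four times a year, or more often if needed. In its paragraph on the phase III board it also refers to an automatic hold on enrolment within a cohort or before the next one, with no number.

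**The concern.** The 5-patient look stops accrual and waits. The second limit has no such mechanism: the places that say when it is read point to a full cohort, and suspending a cohort that is already full does little for accrual. If the fourth major toxicity came to light when 12 patients were enrolled, nothing with a number attached would halt enrolment before patient 30.

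A toxicity count can only rise. Once it exceeds the limit, further patients cannot alter the outcome that the plan attaches to the limit, which is suspension and review. They would be enrolled on a dose that had already failed the plan's own criterion. At the planned 10 patients per month, the remaining 25 patients enrol in about 25/10 = 2.5 months, so stage 2 could fill between two quarterly DSMC reviews.

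**Working it through.** **Inputs.** Section 14.1.1.5: 5 patients, suspend at 2 or more; 30 patients, suspend at 4 or more (Cohort A) or act at 3 or more (Cohort B); toxicity assessed at end of treatment. Section 14.1.1.4: 10 patients per month; an unacceptable rate of 15%, tested "using a one-sided 10% level exact binomial test in each dose level". Section 5.3: 56 days of treatment.

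**Step 1: reproduce the printed table.** With X5 and X25 the event counts in the first 5 and next 25 patients at true rate p:

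P(suspend) = P(X5 ≥ 2) + P(X5 = 0)·P(X25 ≥ 4) + P(X5 = 1)·P(X25 ≥ 3)

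- p = 5%: 0.0226 + 0.7738 × 0.0341 + 0.2036 × 0.1271 = 0.0226 + 0.0264 + 0.0259 = 0.075
- p = 15%: 0.1648 + 0.4437 × 0.5289 + 0.3915 × 0.7463 = 0.692

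| True rate | After 5: computed (printed) | By end: computed (printed) |
|---|---|---|
| 5% | 0.0226 (0.023) | 0.0749 (0.075) |
| 10% | 0.0815 (0.081) | 0.3729 (0.373) |
| 15% | 0.1648 (0.165) | 0.6916 (0.692) |
| 20% | 0.2627 (0.263) | 0.8831 (0.883) |
| 30% | 0.4718 (0.472) | 0.9912 (0.991) |

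The complements at 5% and 15%, 92.5% and 30.8%, are the stated chances of proceeding. The plan's arithmetic is sound.

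**Step 2: suspend at the crossing event.** A cohort that passes the first look reaches a fourth event at some patient from 6 to 30 if and only if it has at least four events among its 30. The two rules therefore suspend the same cohorts. An exact patient-by-patient recursion gives identical probabilities at every rate in the table (differences below 1e-15).

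**Step 3: patients enrolled after the crossing.** The documents do not say when an event enters the count, so three assumptions bracket it. Stage 2 accrual is simulated at 10 per month; the known-at-once case is exact. Means are among cohorts that cross in stage 2.

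| Event enters the count | 15% | 20% | 30% | 40% |
|---|---|---|---|---|
| At day 56 | 0.25 | 0.4 | 0.9 | 1.5 |
| Evenly over 56 days | 2.4 | 3.5 | 6.0 | 8.4 |
| At once | 8.8 | 10.6 | 14.2 | 16.9 |

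The day-56 row is small because 56/30.4 × 10 ≈ 18 of the 25 stage 2 patients are enrolled before the first of them finishes treatment.

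A cohort crosses in stage 2 with probability 0.052, 0.527 and 0.620 at true rates of 5%, 15% and 20%. Averaged over all cohorts opened, even spread gives about 0.06, 1.3 and 2.2 patients at those rates. If accrual ran at half the planned rate (an assumption), the conditional means at 15/20/30/40% would be 5.0/6.5/9.8/12.4 with even spread and 2.4/3.4/5.7/7.9 with day-56 counting.

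**Step 4: Cohort B.** Replacing 4 by 3 in the formula gives 0.194 at 5% and 0.851 at 15%. The printed table does not cover this limit.

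**Step 5: the D-dimer test.** Power by the noncentral t, with effect 0.2, SD 0.3 and one-sided 0.05 (Section 14.1.1.4), is 0.97 with 30 patients and 0.89 with 20.

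**The case against.** **The text may already mean a running count.** Suspending a cohort makes most sense while it is accruing, and Section 12.2 speaks of an automatic hold within a cohort. A reader might infer from the table label that the plan definitely lets a failing cohort run to 30; the documents do not go that far. What stands is that the label, the stated time of evaluation and Section 5 all favour the end-of-cohort reading. The hold in Section 12.2 has no number and could refer to the 5-patient look.

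**Events would not go unseen.** Serious events reach the overall principal investigator within one business day (Section 11.4.1), and the DSMC can meet more often. This is a real safeguard, but it relies on discretion where a count could act. It also makes pure day-56 knowledge unlikely for many events.

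**The gain may be small.** With day-56 counting, about 92% of Cohort A cohorts crossing at a 15% rate would have no patient affected. The largest gains occur at 30–40%, at least twice the rate the plan calls unacceptable, where the first look already stops 47–66% of cohorts. This stands, so the size must be given as a range.

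**Later patients are not uninformative.** A reader might infer that patients enrolled after the crossing contribute nothing and that the change is free in every respect. Neither holds. Suspension leads to a review of detailed data, which later patients inform, and they also count towards the D-dimer test and the 60-patient VTE rule. The no-cost result concerns the toxicity rule alone.

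**Cohort B is different.** A reader might carry the same rewording over. There, crossing the limit restricts the phase III dose and is not said to suspend accrual, so a hold would be a new rule.

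**Conclusion.** The point holds for Cohort A on the most natural reading: the full-cohort limit is tied to 30 patients, and no numbered count holds accrual between patients 6 and 30. That suspending at the crossing event leaves the probability of suspension unchanged is exact and holds for any limit finally adopted.

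The benefit is uncertain. At 10 patients per month it runs from well under one patient (day-56 counting, 15%) to about 9–17 patients (known at once, 15–40%) per cohort that crosses in stage 2. Even spread over 56 days, an assumption the documents neither support nor exclude, gives about 2–8.

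The downside is limited. A cohort suspended and then closed has fewer patients for D-dimer and VTE, but only cohorts that would reach the same suspension anyway are affected, and not if review reopens accrual.

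The limits themselves disagree. Section 5 uses one or more in the first 5 and three or more for the step to Cohort B. Section 14.1.1.5 uses more than one and more than three for Cohort A, and three or more for Cohort B. No view is taken here on which is right.

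**What to change.** 1. **Cohort A, Section 14.1.1.5:** state that accrual is suspended for DSMC review as soon as the number of major toxicities exceeds the full-cohort limit, at whatever point in the cohort this occurs. Relabel the second table row *probability of stopping during or at the end of the cohort*. Its figures stay as printed if the present limit is kept.
2. **Timing:** say when an event enters the count (when reported, or at end of treatment), since the benefit depends on it.
3. **Section 12.2:** tie the automatic hold to this trigger by cross-reference and make clear which committee acts in phase II.
4. **Cohort B:** state whether crossing its limit also holds accrual. If so, print its own stopping probabilities.
5. **Limits:** reconcile Sections 5 and 14.1.1.5, and recompute the table if the adopted limit differs from the one it now uses.

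For Cohort A the cost is one sentence, one label and a cross-reference: no extra patients and no change in the toxicity rule's error rates. The possible price is a smaller D-dimer and VTE sample in a cohort that the DSMC then closes.

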- 14.1.2 The primary aim of the **phase III trial** is determine whether isoquercetin reduces the cumulative incidence of symptomatic or proximal VTE in cancer patients at 56 days.
 - 14.1.2.1 **Study design:** The trial is a randomized, placebo-controlled, doubleblinded phase III trial. Study subjects are randomized to placebo or isoquercetin. The structure of the study matches the phase II study, the central differences being that VTE is the primary endpoint and a single isoquercetin arm is compared to placebo.
 - 14.1.2.2 **Randomization:** Central randomization (1:1) will be performed by QACT Office at DF/HCC and stratified by cancer diagnosis and institutions.
 - 14.1.2.3 Accrual: Anticipated accrual is 20 patients per month across all sites.

14.1.2.4 Sample size justification:

The overall incidence of thrombosis in cancer populations varies between 2-40% based on histology, stage, chemotherapeutics, additional risk factors and mode of surveillance (imaging or symptomatic events). The overall cumulative incidence of VTE in recently conducted MicroTEC study with similar eligibility criteria and study design was 11.3%. The estimate of isoquercetin benefit is based on data from primary thromboprophylaxis trials that typically achieve VTE rates of 4% or less.^{60,61} Based on the estimated VTE rates of 11% in the placebo and 4% isoquercetin arms, a total of 281 isoquercetin-treated subjects and 281 placebo-treated subjects would be required to reject the null hypothesis that the failure rates for experimental and control subjects are equal with probability (power) 0.85. The 1-sided type I error probability associated with this test of this null hypothesis is 0.025. In order to adjust for death or dropout of 5% prior to 56 days, the sample size is increased by an additional 28 patients. We plan an interim analysis for efficacy or futility after 50% of patients have been randomized that will be guided by O'Brien-Fleming boundaries. This will require an additional increase in sample size of 5% or 28 patients. Therefore, we plan to enroll a total of 618 patients. A total of 30 patients enrolled in the phase II trial will be included in the total accrual target and final VTE endpoint analysis.

14.1.3 Primary endpoint analysis will be performed on an intention to treat basis following randomization for all patients who undergo baseline assessment for the presence of VTE and at least one dose of study medication. The cumulative incidence of VTE

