- Fine and Graey regression modelling will be performed to assess the influence of chemotherapy, blood counts, growth factors, ECOG performance status on VTE risk.
- Quality of Life (QOL) will be assesses using EORTC QLQ-30 version 3 which is an internationally validated and widely utilized questionnaire.⁵⁷ Scoring is based on responses to 30 questions dealing with functional quality and symptom burden. The questionnaire will be completed at baseline visit and end of treatment assessments. All are reported on a range 0-100; a high score represents a high level of functioning and QOL. We will analyze the data using analysis of variance techniques if the QoL has constant variance across groups (based on VTE rates and treatment groups). If not, we will use the Kruskal-Wallis test based on ranked QoL scores. If the questionnaire developers provide guidelines for scoring in the presence of missing data, we will

follow those guidelines. Alternatively, we will tally the number of questionnaires for which a particular data item is missing.

- Correlation between isoquercetin dose, plasma PDI inhibitory activity, and reduction in D-dimer or VTE incidence
- Cumulative incidence of VTE according to Khorana score³⁷
- At completion of phase II portion, we will compare the cumulative incidence of VTE of all 60 patients enrolled with similar historical population. As described above the overall cumulative incidence of VTE with similar inclusion criteria and design was 11%. We hypothesize the cumulative incidence of VTE in the phase II cohort will be 4%. Based on these assumptions, the power for this comparison is 80% (N=60 with a 1-sided alpha of 0.1 comparing 4% to historical 11% cumulative incidence rate using a Fisher exact test.)

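### The fallback rule for considering phase III (9 or fewer VTE of 60) is set against 10% and 25%, not the protocol's own 11% versus 4%: once it is used, a drug with no effect at 11% is labelled promising 88% of the time

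*Combined protocol and SAP*

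**What the plan says.** Section 14.1.1.7 makes the D-dimer result the main guide to phase III. If neither cohort shows a significant reduction, "consideration to advance to phase III will be made based on overall VTE rate in the combined isoquercetin arms". The section explains that isoquercetin might prevent thrombosis without changing D-dimer. A true VTE rate below 10% counts as promising, "whereas a true cumulative incidence rate of 25% would not be worthy of further study", and the rule is "Treatment is considered promising among the 60 patients treated with isoquercetin when nine or fewer VTE are observed". Its properties are given at two rates only: "at least a 92% chance of concluding the treatment is effective" when the true rate is 10%, and less than 5% when it is 25% or more. The section attributes these figures to a Fisher exact test and gives no source for the 25%.

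Two other sections use different rates:

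- Section 14.1.2.4 sizes phase III thus: "Based on the estimated VTE rates of 11% in the placebo and 4% isoquercetin arms". The 11% rests on 11.3% in an earlier trial that the protocol describes as similar in eligibility and design.
- Section 14.2 plans a comparison of all 60 phase II patients with history when phase II is complete: "As described above the overall cumulative incidence of VTE with similar inclusion criteria and design was 11"%, and "We hypothesize the cumulative incidence of VTE in the phase II cohort will be 4"%. It uses one-sided alpha 0.1 and states 80% power.

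Nothing in 14.1.1.7 refers to the 14.2 comparison, and nothing in 14.2 says that it bears on the decision.

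**The concern.** A go rule should be much more likely to pass a drug with the hoped-for effect than a drug with none. Here the rate called promising (10%) is almost the rate that the protocol expects without any benefit (11%). The rate that the rule guards against (25%) is more than twice that. Error is controlled only where the protocol does not expect the truth to lie.

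The fallback comes into play only after both D-dimer tests have failed, when the VTE count is the stated basis for considering phase III. The planned trial has 618 patients, of whom 30 are carried over from phase II, so 588 would be new. If the label appears nearly as often without an effect as with one, it adds little to that decision. Yet 14.1.1.7 words it as a conclusion that the treatment is effective.

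**Working it through.** **Inputs.** n = 60 and cut-off 9 (14.1.1.7); benchmark rates 10% and 25% (14.1.1.7); 11% and 4% (14.1.2.4 and 14.2); one-sided alpha 0.1 (14.2); 5% death or dropout (14.1.1.4). The rates of 15% and 20% below are sensitivity values chosen for this check; the documents do not assume them for this population.

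**Formula.** With X the number of patients with VTE and p the true rate, P(label) = P(X ≤ c) = Σ from k = 0 to c of C(60, k) p^k (1 − p)^(60 − k).

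**Step 1: the plan's own figures, c = 9.** At p = 0.10 the result is 0.9269 (stated: at least 92%). At p = 0.25 it is 0.0452 (stated: less than 5%). Both reproduce. They come from a one-sample binomial against a fixed rate; a Fisher exact test compares two observed groups, and there is no second group here.

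**Step 2: the same rule at the protocol's planning rates.** The cut-off is 9/60 = 15% observed, above 11%.

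| True rate | P(9 or fewer of 60) |
|---|---|
| 4% (planned benefit) | 99.99% |
| 10% | 92.7% |
| 11% (no effect) | 88.1% |
| 11.3% (source trial) | 86.5% |
| 15% (sensitivity only) | 58.8% |
| 20% (sensitivity only) | 21.3% |
| 25% | 4.5% |

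The label is 0.9999 / 0.8813 = 1.13 times as likely with the planned benefit as with no effect. P(label) falls to 10% only at a true rate of about 22.6%.

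**Step 3: cut-offs that fit 11% versus 4%.**

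| Cut-off | At 11% | At 4% | At 6% |
|---|---|---|---|
| 3 or fewer | 9.2% | 78.1% | 51% |
| 4 or fewer | 19.7% | 90.8% | 71% |
| 9 or fewer (current) | 88.1% | 99.99% | 99.7% |

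The largest cut-off that keeps the 11% column at or below 10% is 3. Its likelihood ratio is 0.781 / 0.092 = 8.5.

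**Step 4: two messages from one dataset.** An exact one-sample version of the 14.2 comparison rejects 11% only at 3 or fewer. With 4 to 9 VTE, 14.1.1.7 says promising while that test does not reject. The chance of such a count is 0.8813 − 0.0920 = 78.9% at 11%, and 0.9999 − 0.7813 = 21.9% at 4%.

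**Step 5: evaluable number.** With 5% loss, 60 × 0.95 = 57. Keeping 9 then gives 90.9% at 11%, and 6.8% at 25%, which is above the stated 5%. Keeping 3 gives 11.4% at 11% and 80.6% at 4%.

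**The case against.** The strongest reply is that this is a disclosed screening choice. The rule states its benchmarks and computes its properties correctly. It is meant to rule out a clearly bad VTE rate, and since it exists because D-dimer may miss an effective drug, leaning towards sensitivity is defensible. The 14.2 comparison with 11% will also be available at the same time. Much of this stands. It does not explain why the no-effect rate is 11% in two places and 25% in a third, and 14.1.1.7 gives neither a sensitivity argument nor the rule's behaviour at 11% or 4%. The 14.2 comparison is not tied to the decision.

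The 11.3% came from a trial in which some patients received low molecular weight heparin (section 2.2), so the untreated rate may be higher and the 88% correspondingly lower. That is a fair limit. But if the sponsor believes in a much higher rate, 14.1.2.4 and 14.2 need it too.

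Four stronger readings are not supported:

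- *That an ineffective drug has an 88% chance of reaching phase III.* The figure applies only once both D-dimer tests have failed, and only to the label. The principal investigators decide (14.1.1.7), the protocol must be amended (section 5), and phase III has an interim look for efficacy or futility (14.1.2.4).
- *That the untreated rate can be put at 12 to 17% from the high-microparticle patients.* The product 45% × 27–38% relies on a 27% observed in 11 patients and on an upper figure that may reflect longer follow-up. Section 14.2's own planning rate for such patients on placebo is 20%, and 45% × 20% = 9%, which is compatible with 11% overall.
- *That the carry-over of 30 phase II patients into the final analysis shows the rule to be harmful.* That is a separate question. On a simple calculation (309 per arm, 30 isoquercetin patients from phase II, both arms at 11%, pooled z-test, no interim look), selection by the current rule moves the one-sided error only from 2.5% to 2.7%. A cut-off of 3 would raise it to 4.4%.
- *That 3 is the only correct cut-off.* Choosing 3 or 4 is a trade-off between false labels and missed benefit.

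**Conclusion.** The concern holds, at moderate weight. The arithmetic in 14.1.1.7 is right; the benchmarks conflict with those in 14.1.2.4 and 14.2. On the protocol's own rates, a drug without effect is labelled promising 88.1% of the time once the fallback is used, against 99.99% for a drug with the planned benefit, so the label carries almost no information about which is true. This assumes a no-effect rate of 11%, all 60 patients evaluable, and independent yes/no outcomes. If the untreated rate is higher, the rule discriminates better: P(label) without effect is 59% at 15% and 21% at 20%. The documents give no untreated-only rate to choose between these.

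**What to change.** In 14.1.1.7:

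1. Replace the 10% and 25% benchmarks with the 11% versus 4% contrast already planned in 14.2, and say that this contrast governs the fallback. Alternatively, justify another untreated rate, use it in 14.1.1.7, 14.1.2.4 and 14.2 alike, and derive the cut-off from it.
2. Name the exact one-sample binomial in place of the Fisher exact test.
3. State the probability of the label at 4% and 11% for the chosen cut-off, and recompute it for the number actually evaluable.

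At 14.2's one-sided alpha of 0.1 the cut-off is 3 or fewer of 60. If the sponsor prefers sensitivity, 4 or fewer is arguable. If 9 is kept, report the 88% at 11% and stop describing the label as a conclusion of effectiveness.

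The change is to wording, with no extra phase II patients, but a stricter screen has a price. At a true 6%, the drug would be called promising 51% of the time with 3 or fewer and 71% with 4 or fewer. Power at 4% with a cut-off of 3 is 78.1%, slightly below the 80% stated in 14.2. With 57 evaluable, holding alpha strictly at 10% forces a cut-off of 2, with 4.2% at 11% and 60.0% at 4%. The carry-over of 30 patients should be settled separately, but re-examined if the cut-off is tightened.
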